- 2. Previous diagnosis or treatment for ADHD or any neurologic condition other than multiple sclerosis (e.g., traumatic brain injury, epilepsy)
- 3. clinical relapse of MS within 60 days of screening,
- 4. change in disease-modifying therapy within 90 days of screening,
- 5. below average estimated premorbid intelligence (WTAR score #16th percentile),
- 6. severe cognitive impairment indicated by a Mini Mental Status Examination (MMSE) < 24/30,
- 7. contraindications for atomoxetine use: (a) self-reported history of suicidal ideation within the last twelve months (Columbia Suicide Severity Rating Scale), (b) diagnosis of bipolar illness, (c) moderate or severe current depressive symptomatology (Beck Depression Inventory Fast Screen # 9), (d) diagnosis of hepatic disease, (e) narrow angle glaucoma, (f) pheochromocytoma, (g) monoamine oxidase inhibitor within 14 days of study drug start, (h) taking strong CYP2D6 inhibitors (e.g., paroxetine, fluoxetine, quinidine), (i) diagnosis of heart disease, (j) pregnant or planning pregnancy during the study period, (k) breastfeeding, (l) hypersensitivity to atomoxetine or component of formulation. Note that in the case where a potential subject is receiving medication for care that interacts with atomoxetine, her / his clinical regiment will not change to allow for study entry.

Enrollment Restrictions Based Yes
Upon Gender, Pregnancy,
Childbearing Potential, or Race

Justify Restriction(s)

We are excluded women who are pregnant or planning to become pregnant during the study period. Pregnancy risk associated with atomoxetine is category C (risk cannot be ruled out).

Age Range(s) 18 to 64 Years
Targeted Population(s) Adults - Patients

Other Aspects that Could Increase Subjects Vulnerability

None.

Safeguards to protect Subjects rights and welfare

We are employing inclusion / exclusion criteria which minimize risk to patients from atomoxetine, and we will monitor side effects. We will also emphasize the voluntary nature of this study, and that there is no penalty for withdrawal.

9. Subjects - Participation

Duration of an Individual Subjects Participation in the Study

Once consented and screened, the baseline will be completed and the rest of the study will take fourteen weeks: sixweek phase one, two-week washout, six-week phase two.

Duration Anticipated to Enroll All Study Subjects

One year

Estimated Date for the Investigators Within one year to Complete This Study

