After informed consent, subjects will engage in a 30-minute screening consisting of memory tests (Rey Auditory Verbal Learning Test, Visual Reproduction of the Wechsler Memory Scale, Fourth Edition), word-reading test (Weschler Test of Adult Reading), depressive symptoms (Beck Depression Inventory, Fast Screen), and assessment of suicidal ideation within the past twelve months (Columbia Suicide Severity Rating Scale).

Patients who meet all inclusion criteria will advance to the fourteen week crossover trial.

- 1. Baseline Evaluation:
- a. Memory Tests: Selective Reminding Test, Brief Visuospatial Memory Test, Revised, CANTAB Paired Associate Learning, NIH Toolbox Picture Sequence Memory Test (PSMT)
- b. Cognitive Efficiency Tests: Symbol Digit Modalities Test, CANTAB Rapid Visual Information Processing, Woodcock Johnson Reading Fluency, WAIS-IV Digit Span
- c. Questionnaires: Perceived Deficits Questionnaire (self-report of cognitive/memory deficits), Beck Depression Inventory, Fast Screen (mood), Fatigue Severity Scale (fatigue), Columbia Suicide Severity Rating Scale (suicidal ideation)
- d. Motor Tasks: 25-foot walk, Nine Hole Peg Test

2. Phase One Drug:

Patients will receive atomoxetine or identically encapsulated placebo from the research pharmacy. They will receive two containers: one containing seven 40mg capsules, and one containing enough 80mg capsules for the remaining five weeks. Subjects will be instructed to take the 40mg dose once per day (in the morning) for the first seven days, and then switch to the 80mg dose once per day (in the morning) for the remainder of Phase One. Subjects will be encouraged to set an alert in their smartphones to remind them to take the capsule at the same time each day. Subjects will also be provided with information about atomoxetine (Strattera) provided by the pharmaceutical company (Eli Lilly). Patients will be instructed not to take more than one capsule per day. If they miss a dose, they should keep it in the container. All remaining capsules will be returned to the investigator at the end of the six weeks (when the subject returns for the first follow-up). Patients will also be instructed to contact the study team immediately if they experience any side effects.

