3. Phase One Evaluation: The baseline evaluation will be repeated on the last day of Phase One. Alternate forms will be used as appropriate. In addition, patients will be asked to guess which type of capsule they were tasking, and also complete an additional questionnaire:

Patient-Reported Memory Change: Patients will endorse global memory change over the past month as: much improved (3), somewhat improved (2), mildly improved (1), unchanged (0), mildly worse (-1), somewhat worse (-2), much worse (-3).

4. Two week washout period.

Patients will go two weeks without taking any study capsule.

5. Phase Two Drug

The same procedures as Phase One will be followed, except that patients will receive the opposite capsules as Phase One.

6. Phase Two Evaluation

The same procedures as the Phase One Evaluation will be repeated.

Description of the Source Records that Will Be Used to Collect Data About Subjects

Paper source records will include demographic information, general medical history, and MS medical history information; however, there will be no PHI on any source forms. All data will be collected using paper neuropsychological record forms and/or score sheets. CANTAB tasks are performed on an iPad; however, no PHI will be entered into the iPad. Instead, CANTAB scores will be transferred to paper score sheets. All data will be entered into a RedCap database, which will include no PHI.

Description of Data that Will Be Collected Including Long-Term Follow-Up

This is documented above.

Research Requires HIV Testing

Page 15 of 32

11. Procedures - Genetic Testing

Genetic Testing Will Be Performed No
Guidance and Policies > Future Use Data Sharing and Genetic Research

Page 16 of 32

12. Procedures - Details

Surveys or Interviews Yes

Type of Instruments Being Used Standardized, Created By Research Team

Names of Standardized Instruments

NEUROPSYCHOLOGICAL INSTRUMENTS

Rey Auditory Verbal Learning Test

Visual Reproduction of the Wechsler Memory Scale

Brief Visuospatial Memory Test, Revised

Selective Reminding Test

CANTAB Paired Associate Learning

NIH Toolbox Picture Sequence Memory Test

Symbol Digit Modalities Test

CANTAB Rapid Visual Information Processing

Woodcock Johnson IV Reading Fluency

Wechsler Adult Intelligence Test, Third Edition: Digit Span

Wechsler Adult Reading Test

25-Foot Walk

Nine Hole Peg Test

QUESTIONNAIRES

Perceived Deficits Questionnaire

Beck Depression Inventory, Fast Screen

Fatique Severity Scale

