Data will be stored in a locked filing cabinet located in a locked closet, within a locked office (PI: [name]). Each lock has a separate key. Only two persons have the key to the filing cabinet: [name] (PI) and the study research coordinators. Data files will be kept separate from identifiable data (PHI), with the exception of a password protected and encrypted Excel file linking subject names and subject numbers. This file will be located on a ISMMS network drive and only accessed from ISMMS computers. Only [name] and the coordinators will have the password. Raw data files may be retrieved by [name] or the research coordinator, and viewed on site in a private office space. Files will not be removed from Mount Sinai Hospital. Files will be immediately returned to their secure location within the filing cabinet.

Power Analysis/Data Analysis Plan (Including Any Statistical Procedures)

[name] will lead statistical analyses, which will consist of dependent T-tests comparing differences in outcomes (e.g., memory composite score) between the drug and placebo phases of the cross-over trial.

20. Data - Safety Monitoring

More Than the Minimum Data Yes Safety Monitoring Will Be Done

Principal Monitor [name]

Additional Monitors

Specific Items That Will Be Monitored for Safety

Suicidal ideation will be monitored with the Columbia Suicide Severity Rating Scale. Subjects who report suicidal ideation at any point in the study will be escorted to the psychiatric emergency department at Mount Sinai Hospital for further evaluation.

Suicidal ideation and other adverse events reported by patients will be recorded. Co-I [name] [name]. will review all adverse events as they are reported, and judge severity. [name] is not involved in data collection or processing, so she can be unblinded to identify whether adverse events occurred during atomoxetine or placebo.

Frequency of Data Review

Suicidal ideation will be evaluated at baseline, first follow-up, and second follow-up for all subjects, and immediate action will be taken if suicidal ideation is present (as noted above).

[name] will also be told immediately of any other serious adverse events, such as allergy to atomoxetine. She will have access to condition assignments in the case of adverse events.

Rules for Alteration of Study Design

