After twelve subjects have been completed the trial, [name] will evaluate whether serious adverse events are more likely during atomoxetine or placebo. If serious adverse events are 2:1 more likely during atomoxetine, the study will be halted.

Selection Procedures to Minimize Toxicity

We are using the recommended dosage of atomoxetine based on prescribing information in the package insert. Also, we are excluding patients taking strong CYP2D6 inhibitors (e.g., paroxetine, fluoxetine, quinidine), which minimizes risk of toxicity.

Grading System to Evaluate Adverse Events

Serious adverse events will include suicidal ideation and allergy to atomoxetine.

Other adverse events include constipation, upset stomach, difficulty sleeping, dry mouth, loss of appetite, irregular periods, decrease in sexual function, urinary hesitancy sweating, and dizziness.

Procedures to Assure Data Accuracy

All adverse events reported to the research team at any time in the study (including the three assessment phases) will be recorded for frequency and severity. Severity will be judged my our study physician, [name] [name]. These will be documented in a study RedCap database, and will be reported for each condition (atomoxetine, placebo) with the study results. [name] will also be able to determine subject condition in the event of serious adverse events.

Suspension Reported to

Suspension would be reported the the IRB.

Anticipated Circumstances of Subject Withdrawal

Subjects would be withdrawn from the study if they experience any severe adverse events. Of course, subjects may choose to withdraw at any time without penalty.

Primary or Secondary Safety Endpoints

Primary safety outcome will be suicidal ideation.

Secondary safety endpoints include constipation, upset stomach, difficulty sleeping, dry mouth, loss of appetite, irregular periods, decrease in sexual function, urinary hesitancy sweating, dizziness, and allergy to atomoxetine.

Data Monitoring Committee Description

DMC.docx

DMC Charter Available

21. Funding

Funding Source Name National Multiple Sclerosis Society

Contact

Funding Category Foundation

Meditrack (https://contracts.tractmanager.com/Contracts/Login.aspx)

Grant or Contract Title Pilot Randomized Controlled Trial of Atomoxetine to Treat Memory Impairment in MS

Patients

Grant or Contract

Number

PP-1606-24739

Funding Status Funded **Project Initiated By** Investigator

Grant / Contract Principal [name]

Investigator (PI)

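### About ten symptoms are secondary safety endpoints to be reported by condition, but no evaluation asks about them, there is no systematic baseline, and no rule separates new from existing symptoms

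*Combined protocol and SAP*

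**What the plan says.** The endpoints are listed in section 20 (Data - Safety Monitoring), under Primary or Secondary Safety Endpoints: "Secondary safety endpoints include constipation, upset stomach, difficulty sleeping, dry mouth, loss of appetite, irregular periods, decrease in sexual function, urinary hesitancy sweating, dizziness", followed by allergy to atomoxetine. Under Procedures to Assure Data Accuracy, adverse events are to be recorded with frequency and severity, severity is judged by the study physician, and results are given separately for atomoxetine and placebo.

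Four statements bear on how these events reach the record:

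- Section 20, Procedures to Assure Data Accuracy, opening sentence: "All adverse events reported to the research team at any time in the study (including the three assessment phases) will be recorded".
- Section 20, Specific Items That Will Be Monitored for Safety: "Suicidal ideation and other adverse events reported by patients will be recorded".
- Section 10 (Procedures - Narrative), Phase One Drug: "Patients will also be instructed to contact the study team immediately if they experience any side effects".
- Section 8, on safeguards for subjects: "we will monitor side effects", with no method or schedule.

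The visit content is in section 10. The baseline self-report measures are given as "Questionnaires: Perceived Deficits Questionnaire (self-report of cognitive/memory deficits), Beck Depression Inventory, Fast Screen (mood), Fatigue Severity Scale (fatigue"), plus the Columbia Suicide Severity Rating Scale. For follow-up, "The baseline evaluation will be repeated on the last day of Phase One", and the additions are these: "In addition, patients will be asked to guess which type of capsule they were tasking, and also complete an additional questionnaire". That questionnaire is the memory-change rating. The phase two evaluation follows the same procedures.

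**The concern.** An endpoint that is to be compared between conditions needs a measurement that every patient receives in the same way in each condition. Suicidal ideation, the primary safety outcome, has one: a named scale given to all subjects at baseline and both follow-ups. The secondary safety endpoints have none. As written, there is no denominator of patients who were asked, so the absence of a report cannot be read as the absence of the symptom.

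Three things follow. Symptoms that patients are reluctant to raise, such as sexual or urinary ones, are likely to be undercounted. What patients raise may depend on expectation, because they are given the manufacturer's information on atomoxetine and form a view of which capsule they have. And a complaint that predates the study drug can be entered as an adverse event, since nothing requires a comparison with baseline.

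The lay summary says the results will inform planning of a possible phase 3 trial. By-condition side-effect rates would be part of what that planning has to work with.

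**Working it through.** **1. Count of endpoints.** Reading the unpunctuated urinary hesitancy and sweating as two items gives ten symptoms; reading them as one gives nine. Allergy is additional.

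**2. Endpoints set against visit content.** The baseline battery in section 10 consists of memory tests, cognitive efficiency tests, the Perceived Deficits Questionnaire, a depression screen, a fatigue scale, the suicidality scale and two motor tasks. The follow-ups add a capsule guess and the memory-change rating. The instrument list in section 12 adds no side-effect checklist. None of the instruments is described as a measure of the listed symptoms. The analysis plan names dependent t-tests and gives no method for adverse event rates. No rule assigns an event that begins in the two-week washout to a condition.

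**3. Size, by illustration.** The documents state no adverse event rate, capture rate or pre-drug symptom frequency, so there is no plan figure to reproduce and every rate below is an assumption. Let *p* be the true new-onset rate (30% on atomoxetine, 10% on placebo), *c* the share of events captured, and *b* the share of patients with a persistent pre-existing symptom. Then

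observed rate = c × [b + (1 − b) × p].

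For example, with c = 1 and b = 0.2: 0.2 + 0.8 × 0.30 = 44%, and 0.2 + 0.8 × 0.10 = 28%. The last column is the power of a two-sided exact McNemar test at 5% with n = 24, taking responses as independent between periods given baseline status.

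| c | b | Atomoxetine | Placebo | Difference (points) | Ratio | Power |
|---|---|---|---|---|---|---|
| 1.0 | 0 | 30% | 10% | 20 | 3.00 | 26% |
| 0.7 | 0 | 21% | 7% | 14 | 3.00 | 13% |
| 0.5 | 0 | 15% | 5% | 10 | 3.00 | 5% |
| 0.3 | 0 | 9% | 3% | 6 | 3.00 | 1% |
| 1.0 | 0.2 | 44% | 28% | 16 | 1.57 | 17% |
| 1.0 | 0.4 | 58% | 46% | 12 | 1.26 | 9% |
| 0.5 | 0.2 | 22% | 14% | 8 | 1.57 | 4% |

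In patients, full capture with no prior symptoms gives 24 × 0.30 = 7.2 against 24 × 0.10 = 2.4. At 30% capture this becomes 24 × 0.09 = 2.2 against 24 × 0.03 = 0.7.

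Uniform under-capture shrinks the difference and leaves the ratio alone. Pre-existing symptoms raise both rates and pull the ratio toward 1.

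**4. Expectation.** Suppose a symptom occurs in 20% of both phases, every patient guesses the capsule correctly, and affected patients report it 60% of the time when they suspect drug and 30% when they suspect placebo (all assumed). The record shows 0.20 × 0.60 = 12% against 0.20 × 0.30 = 6%, a twofold excess with no drug effect.

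**5. What a baseline rule recovers.** With b = 0.2 and full capture, counting only new symptoms gives 0.8 × 0.30 = 24% against 0.8 × 0.10 = 8% of all patients. The ratio returns to 3.0. This ignores worsening of symptoms already present.

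**The case against.** A reader might infer more than the documents support, in five ways.

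- **That only volunteered events will be captured, and that undercounting is certain.** The documents do not say that staff will refrain from asking, and reports made at the assessments are to be recorded. How events are elicited is unspecified. Undercounting is likely, not established.
- **That nothing is known at baseline.** The recording statement covers all three assessments, including baseline, and the source records hold general and MS medical history. A complaint mentioned at baseline would be kept. What is missing is a systematic, symptom-by-symptom baseline and a rule for using it.
- **That existing symptoms bias the contrast toward one condition.** Each patient is meant to take both conditions, so a stable symptom enters both periods. It dilutes the ratio but does not by itself favour either condition.
- **That existing symptoms are known to be common here.** The documents give no frequency for this population; 20% and 40% are assumptions.
- **That tolerability is a stated aim.** Both objectives concern cognition, patient-reported function, fatigue and mood, and the primary safety outcome is properly solicited.

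It is also fair to say that a checklist would not make these contrasts decisive: on the assumed rates, power is only 26% even with complete capture and no prior symptoms. Nor would it remove expectation, since checklist answers can also depend on the capsule a patient thinks they have. And asking about known drug effects could prime the phase two memory rating, which is a primary endpoint, and the phase two capsule guess.

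These limits stand, and they narrow the claim. They leave the gap in place: named endpoints, promised by condition, with no stated procedure for measuring them in every patient.

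**Conclusion.** The point holds in limited form. The plan specifies secondary safety endpoints without a uniform way of asking about them, without a systematic baseline and without a new-versus-existing rule. The resulting rates are likely to be too low where patients do not report, may vary with expectation, and would be diluted toward a ratio of 1 where symptoms already exist.

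The size cannot be fixed from the documents. The ranges in the working rest on assumed true rates of 30% and 10%, capture of 30% to 100%, pre-existing prevalence of 0% to 40%, independence between periods and 24 completers. The absence of a symptom measure from the listed visits rests on no assumed rate. Suicidal ideation is not affected. The change is worth making because it is cheap; what it buys is interpretable description, not statistical significance.

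**What to change.** - At baseline and both follow-ups, ask every patient one fixed-wording checklist of the listed symptoms: present or absent, severity, and onset. Use it identically in both periods, and give it after the cognitive tests and, at follow-ups, after the memory-change rating and capsule guess.
- Separate urinary hesitancy and sweating in the endpoint list so that the items can be counted.
- Define the secondary safety endpoints as symptoms new or worse than baseline, reported by condition with the number of patients asked.
- State how an event with onset in the washout is assigned.
- Keep recording spontaneous reports, including allergy, and list them separately.
- Describe the by-condition rates as descriptive.

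The cost is a one-page form and a few minutes at three existing visits. Solicited rates will be higher in both conditions than spontaneously reported ones. Placing the checklist last protects the ratings made at the same visit, but it cannot prevent carry-over to the phase two self-ratings and capsule guess; that possibility should be acknowledged when they are interpreted.
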